If the patient is interested in the study after the discussion of the details of the study and assessment for exclusion criteria, a physician, psychologist, social work investigator, medical student or a trained research assistant will verbally discuss the study in detail and give the patient adequate time to read a written IRB-approved consent form and to ask questions. If they desire, patients will have at least 24 hours to consider enrollment. To ensure that patients have the capacity to provide informed consent, we will ask potential patients to describe their understanding of the study's purpose and their role (e.g., that they understand the timing of interventions and assessments, confidentiality and its limits, our focused review of medical records, and their ability to end participation in the study at any time for any reason). If the patient is about to be discharged and would like more time to review the consent form than is available to them in the hospital, they may take the consent form home to review and send back a signed copy if they ultimately choose to participate in the study. The study team member will also complete with the participant a release of information form that will allow us to contact treaters for information about treatment and outcomes at 12 and 24 weeks. With the help of a member of the study team, the participant will then schedule a visit to the MGH to meet their interventionist, complete baseline questionnaires, and receive their first of three step counters. Participants who enroll in the study, as well as potential participants who choose to take a consent form home to review it further, will receive a brochure that provides additional information about the study.

Consent at baseline visit:

For participants identified through RPDR searches and contacted via opt-out letter and phone call, eligibility will be assessed on the phone. Those participants who appear to be eligible for the study will be scheduled to come to the TCRC at MGH for the baseline study visit. Prior to the visit, a copy of the consent form will be mailed (or e-mailed, if the patient prefers) to the participant. At the baseline visit, a study team member will review the consent form with the participant and ultimately will enroll the patient, as noted above.

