It is exceedingly unlikely that a potential participant will be a patient currently in an investigator's clinical practice; however, if an investigator discovers that a potential participant is a member of his/her clinical practice, an alternate investigator will be substituted to provide a description of the study and obtain informed consent.

Finally, once patients sign the consent form, the investigator will perform a focused review of the patient's medical record (including laboratory data) to again confirm that the patient was admitted for ACS, and will consult with the study cardiologist in the event that there is any need for further clarification. If there is question about the patient's medical prognosis (to assess whether the patient has a condition likely to lead to death within 6 months) the study team will consult with the inpatient or outpatient treatment team and the study cardiologist.

Partners Healthcare has an electronic system that lets the participants' study doctors know if they are admitted to a Partners Hospital, or if they visit a Partners Hospital Emergency Department. We will use this system to ensure that the study doctors know about any possible problems or side effects participants experience while taking part in the study.

C. Treatment assignment/randomization

Participants will be randomized to receive the intervention or MI-based health behavior education (control) arm. They will be randomized by a random-number generator and will be assigned a condition after receiving baseline questionnaires when they return to MGH after discharge. The research assistant (RA)/blinded assessor who will conduct the follow ups will be blind to the study condition. The interventionist and subjects will not be blind to the study condition.

V. Study procedures

A. Study visits (See Table 1)

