After explaining the program, the trainer will introduce to participants how to use a step counter (ActiGraph), and will ask the participant to wear an Actigraph GT3X+ accelerometer for 7 days to make sure they are comfortable using the device and that useable data can be obtained from the participant. ActiGraph accelerometers are validated as measures of physical activity and have been used in numerous studies of physical activity in patients with medical illness.⁷⁰ The accelerometer is a band with a small 1.5” square attached device that is worn around the lower waist, either on a waistband or clipped to the belt or waistband of clothing. It tracks the number

of steps taken. After explaining how to use the devices, the study trainer will schedule an appointment to call the participant in 1 week to review the first exercise over the phone. Lastly, participants in both conditions will also be given a digital pedometer (Omron) that clips on a belt or other article of clothing, to promote and track physical activity.

Table 1. Schedule of study events.

	Pre-enrollment	Week 0	Weeks 1-12	Week 12	Week 24
Cognitive screen	X				
Self-reported adherence (MOS-SAS)	X		X	X	X
Cigarette Use, Alcohol Use (AUDIT-C), Sociodemographic Data		X			
Chart review for baseline characteristics		X			
Self-report measures (DASI, SF-12, LOT-R, SOM, HADS, IPAQ, MEDFICTS, SRMA, PSS-4, PANAS, WISE)		X		X	X
Physical activity (step counter)		X*		X	X

*not used as a baseline measure, but as a way of getting the participant accustomed to the device

Weekly phone sessions (Weeks 1-12). After discharge from the hospital, participants will complete twelve 30-minute weekly phone sessions with a study trainer. The phone sessions primarily will include a review of the prior week's session content and a discussion of the rationale and assignment of the next week's exercise/assignment. These calls will be recorded so that a percentage of these recordings can be reviewed to ensure that both the intervention and control arms of the study are being delivered as described in the protocol and trainer manual.

Positive psychology plus motivational interviewing (PP-MI) condition (intervention)

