Participants will learn about relaxation response exercises and ways to incorporate these exercises into daily life.

Planning for the Future (Session 13)

Participants will review the information learned over the course of the program and think of ways to remain healthy after the end of the program.

Follow-up phone calls (Week 12 & Week 24). At Weeks 12 and 24, a member of the study staff will call participants to repeat most of the self-report questionnaires that were administered at baseline (Week 0). These questionnaires assess adherence to physical activity (a modified version of the IPAQ), adherence to medication (SRMA), and dietary adherence to a low-fat diet (MEDFICTS). Questionnaires will also assess optimism (LOT-R), state optimism (SOM), positive emotions (PANAS), overall health behavior adherence (MOS-SAS), anxiety/depression (HADS), stress (PSS-4), physical functioning (DASI), health-related quality of life (SF-12), and cardiac symptoms (WISE). Participants will also be asked about cardiac-related hospital readmissions and attendance at cardiac rehabilitation, to rate their overall satisfaction with the treatment they received for their cardiac condition (outside of this study) over the last 12 weeks on a scale of 1 (excellent) to 5 (poor), and some questions about ease of use of the study devices. In sum, these scales should take approximately 30-40 minutes to complete.

We will schedule all phone calls during times that are acceptable to participants to reduce intrusions in their lives. We will remind participants of their upcoming study sessions and follow-up phone calls by phone, letter, or e-mail depending on their preference. If participants would rather complete the follow-up questionnaires in written or e-mail form rather than over the phone, we will send them a paper or electronic packet at the time of the follow-up. Participants who choose to complete the follow-up questions through e-mail will be sent a PDF file that will contain no personal identifiable information including name, social security number, address etc. The PDF file will only be labeled with a secure study ID number, and all e-mail communications

will occur via firewalled Partners e-mail accounts (study members' accounts), rather than through outside e-mail servers to protect patient confidentiality.

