Informed consent process. With regard to the consent process, we will approach/recruit participants only after patients' clinicians/floor nurses (who would not be associated with the consent process in any way) ask patients if they are interested in hearing more about an optional study, or through the opt-out letter process described above. If an investigator is clinically caring for a potential participant, an alternate, trained study staff member will approach the patient and complete the informed consent process and all study procedures for that participant. When discussing the study, we will emphasize the study's optional nature and participants' ability to opt out / un-enroll at any time, for any reason. As mentioned above, for participants identified through RPDR searches and contacted via opt-out letter and phone call, those participants who appear to be eligible for the study will be scheduled to come to MGH for the baseline study visit. Prior to the visit, a copy of the consent form will be mailed (or e-mailed, if the patient prefers) to

the participant. At the baseline visit, a study team member will review the consent form with the participant and ultimately will enroll the patient in the same manner as described above.

Medical & psychiatric emergencies. As with any program which promotes an increase in physical activity, there is an inherent potential physical risk imposed (e.g., falls, worsening cardiac symptoms). If participants report acute medical symptoms, they will be directed to emergency medical care, and their primary medical physicians may be contacted as needed. If study staff have questions regarding medical symptoms and their urgency, [name] (co-investigator and cardiologist) and [name] (PI) will be available to consult (and call the participant) as needed. If the participant is having urgent medical symptoms, the study physician(s) will take all needed steps to ensure emergent evaluation, which may include ensuring evaluation in nearest emergency room.

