This study utilizes a questionnaire that assesses depressive symptoms (HADS), and thus, participants might disclose information about suicidal thinking or behavior. Due to this possibility, the follow-up call will be performed at a time when a psychiatrist study investigator is available to intervene as needed. If participants report suicidal ideation, study staff will complete specific suicide risk assessment questions to assess immediate risk of self-harm, and the psychiatrist will immediately assess the situation/participant if there is either an acutely elevated risk of self-harm or if additional information is needed to clarify risk. As with medical issues, if the participant is at imminent risk, the study psychiatrist will take all needed steps to ensure emergent evaluation, which may include ensuring evaluation in the nearest emergency room. Participants will be informed of all of these measures to ensure confidentiality—and the limits of confidentiality, such as arranging for emergent medical or psychiatric care if safety is at imminent risk—as part of the informed consent process. However given that this is a medical rather than a psychiatric population we anticipate the rate of suicidality in this population will be low.

We will ask participants to report adverse events related to study participation they may have experienced at any time throughout the study. Any adverse events will be reported to the PI and to the IRB according to Partners HRC guidelines.

VIII. Potential benefits

A. Potential benefits to participants

It is possible that participants will not receive benefit from participation. It is also possible that they will receive some benefits. Participants will undergo a series of exercises that are designed to increase optimism, improve well-being, and potentially improve cardiac health behaviors. Analyses of PP studies have been that these interventions are associated with improved psychological well-being and decreased depressive symptoms, and optimism is associated with superior medical outcomes. Therefore, participating individuals may benefit by having improvements in these important and clinically relevant outcomes.

Participants also may receive education regarding health behaviors and/or motivational interviewing regarding health behaviors. This may prompt participants to engage in more health

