will also discuss any procedural difficulties, recruitment issues, and adverse events at this meeting (and before if needed). If there are consistent issues with the logistics, feasibility, or acceptability of recruitment, enrollment, follow-ups, or the intervention (e.g., participant complaints about length of follow-ups), we will review our methods and alter the study protocol as needed.

C. Outcomes monitoring

[name] (PI) will review study outcomes after four participants have completed the trial in order to assess the feasibility and acceptability of exercises and to ensure adequate completion of follow-up measures. If participants' completion or follow-up rates are far below the expected rates, if acceptability scores on the exercises are low, if optimism scores decrease following the exercises, or we sense more generally that some participants have been dissatisfied with the program, we will likely alter the protocol to address these issues. Further, we will preliminarily assess outcome measures after 20 participants have completed the study to ensure the feasibility and acceptability remains adequate and to monitor potential outcomes. We will then complete the more formal data analysis once all 48 participants have completed the trial.

D. Adverse event reporting guidelines

We will follow all PHRC guidelines with respect to reporting unanticipated problems, including adverse events. Specifically, when a serious or nonserious adverse event occurs, the PI will review the event to determine if it was possibly or definitely related to participation in the research. For all unanticipated problems and adverse events deemed related or possibly related to the research, we will complete and submit an Other Event report through Insight/eIRB as soon as possible and within 5 working days / 7 calendar days (as defined in the March 2014 Reporting Unanticipated Problems Including Adverse Events report). At Continuing Review, we will provide a summary of all unanticipated problems as per PHRC protocol. Finally, if there are unanticipated problems, especially if serious or recurrent, the PI ([name]) will amend the protocol if it is deemed necessary to protect the safety and welfare of the participants.

X. References

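### Falls and worsening cardiac symptoms are named as risks, but the protocol describes no scheduled cardiac-symptom question between Weeks 0 and 12 and no fall question at any time

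*Combined protocol and SAP*

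**What the plan says.** Section VII.D (Risks, medical and psychiatric emergencies) names two physical hazards of promoting activity: "there is an inherent potential physical risk imposed (e.g., falls, worsening cardiac symptoms".

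The protocol describes these ways of learning of such problems.

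- **A general request (VII.D).** "We will ask participants to report adverse events related to study participation they may have experienced at any time throughout the study". No schedule, form or named event is given.
- **Action on report (VII.D).** "If participants report acute medical symptoms, they will be directed to emergency medical care". The cardiologist and the PI are available for consultation as needed.
- **Electronic alerts (IV.B).** A system lets study doctors "know if they are admitted to a Partners Hospital, or if they visit a Partners Hospital Emergency Department".
- **Follow-up calls at Weeks 12 and 24 (V.A).** The WISE cardiac symptom list is repeated. "Participants will also be asked about cardiac-related hospital readmissions and attendance at cardiac rehabilitation".
- **Contact with treating clinicians (IV.B).** A release form will "allow us to contact treaters for information about treatment and outcomes at 12 and 24 weeks".

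On the twelve weekly calls, V.A says: "The phone sessions primarily will include a review of the prior" week's material, together with the rationale for and assignment of the next exercise. Table 1 marks WISE at Weeks 0, 12 and 24. The only questionnaire it marks for Weeks 1-12 is the MOS-SAS, an adherence scale.

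Once an event is known, IX.D says "the PI will review the event to determine if it was possibly or definitely related to participation in the research". Under IX.B the team discusses adverse events weekly, and the DSMB receives their numbers and rates by arm.

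**The concern.** The participants have had a recent ACS and are being encouraged to move more. The weekly call is the most frequent contact the study has with them, but its described content includes no question on either named hazard.

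The methods that operate between Week 0 and Week 12 all depend on something happening first. The participant must volunteer a symptom, or judge an event to be linked to the study, or attend a Partners hospital. Exertional symptoms that worsen gradually, a fall treated at home, or care at another hospital could pass all three. The wording of the adverse event request matters here: the PI is meant to judge relatedness, but a participant who has already decided that an event is unrelated may never mention it.

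There is also a smaller point on comparability. The DSMB will see adverse event rates by arm, while call content differs between arms by design. PP-MI participants set an activity goal each week. Controls cover several health topics, of which activity is one. Without one common question, it cannot be shown that events were sought equally in both arms.

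**Working it through.** The plan gives no figure to reproduce on this point. The check sets the schedule in Table 1 and V.A against the risks named in VII.D.

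**1. Cardiac-symptom questions.** WISE is specified at Weeks 0, 12 and 24.
- Longest interval, Weeks 0-12: 12 − 0 = 12 weeks, or 12 × 7 = 84 days.
- Longest interval, Weeks 12-24: 24 − 12 = 12 weeks, or 84 days.
- Weekly calls in the first interval: 12. Described symptom items in them: 0.

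**2. Fall questions.** None of the instruments in Table 1 or V.E is described as covering falls. Specified fall questions per participant over 24 weeks: 0.

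**3. What the other routes cover, Weeks 0-12.**

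| Route | Depends on | Leaves open |
|---|---|---|
| Adverse event request | Participant linking the event to the study; no stated timing | Events thought unrelated or not recalled |
| Action on reported symptoms | Participant volunteering them | Symptoms not mentioned |
| Electronic alert | Admission or emergency visit at a Partners hospital | Care elsewhere; problems managed at home |

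Patients recruited in hospital at MGH or BWH need no Partners-affiliated physician (III.A, III.B); that condition belongs to the second recruitment route. Care outside the network is therefore plausible, though the documents give no frequency.

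Cardiac readmissions and persisting symptoms should surface at Week 12, through the follow-up call or contact with treating clinicians. They are more likely to be found late than lost, unless they have resolved or been forgotten.

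**4. With a check on every weekly call.**
- Longest interval in Weeks 0-12: 7 days if all calls take place, 14 days around one missed call.
- Fall questions per participant: 12 weekly + 2 follow-up = 14.
- Weeks 12-24: still 84 days between symptom questions.

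**5. Trainer time.** The assumed length is 1 to 2 minutes of a 30-minute call (1/30 = 3.3% to 2/30 = 6.7%).
- 48 participants × 12 calls = 576 calls. 576 × 1 / 60 = 9.6 h; 576 × 2 / 60 = 19.2 h.
- If 70% of calls take place (assumption, borrowing the Aim 1 exercise-completion target): 403.2 calls, 6.7 to 13.4 h.
- III.B aims to randomize at least 48 and to enroll up to 80. If all 80 were randomized: 80 × 12 = 960 calls, 16 to 32 h.
- Fall question at two follow-ups, 48 participants: 96 × 1 / 60 = 1.6 h.

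**6. Physician time.** The documents give no rate of positive answers. As an assumed range, take 5% to 20% of 576 calls positive, all reviewed by a physician for 10 to 15 minutes.
- Low: 576 × 0.05 = 28.8 reviews × 10 / 60 = 4.8 h.
- High: 576 × 0.20 = 115.2 reviews × 15 / 60 = 28.8 h.

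Sending only acute or unclear answers to a physician would bring this down.

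**The case against.** The strongest reply is that the protocol already has several safeguards and that the weekly calls invite disclosure.

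- PP-MI calls review the previous week's activity goal and work through barriers to activity, and may refer participants to their treatment team. Control Session 3 covers what to ask a physician before becoming active, and Session 5 covers barriers. Any of these could bring out a symptom or a fall. This stands as an opportunity, but none of it is a symptom or fall question.
- The relatedness wording sits in one sentence. The next sentence of VII.D sends any adverse event to the PI, IX.D has the PI review serious and nonserious events, and the SAE definition in IX.B carries no relatedness condition. So the reporting rules are broader than the request. These rules act on events already known; the request still shapes what participants mention.
- The call description says what is primarily included, so it is not exhaustive. Neither the trainer manual nor the consent form is among the documents, and either could contain a prompt. This stands, and it limits the finding to what the protocol describes.
- People who need a walking aid or cannot walk steadily for five minutes are excluded, known events are discussed weekly, and a DSMB gives expedited review of serious events. This lowers the stakes without supplying the question.

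Two stronger readings are tempting. A reader might infer that cardiac problems will be detected 12 weeks late. The documents do not support that: 12 weeks is the wait for the next WISE form, and volunteered reports, weekly contact and Partners alerts can all act sooner. A reader might also infer that adverse event rates will be biased between arms. The gap in collection is the same in both, both receive a pedometer, and whether reporting would differ, or in which direction, is unknown.

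**Conclusion.** The point holds as a cheap improvement. The protocol names two hazards and describes no scheduled, structured question on cardiac symptoms between Weeks 0 and 12, and none on falls at any time. The longest interval between specified symptom questions is 12 weeks. That figure is a worst case, for a problem the participant does not volunteer and that triggers no Partners alert.

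The number of events found late or lost cannot be estimated, because the documents give no rate for falls or unreported symptoms. Nor do they support saying that adverse events go uncollected: a general request exists, and cardiac capture at Weeks 12 and 24 is reasonable.

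The conclusion assumes that the trainer manual holds no equivalent check. If it does, the remaining task is to put that check into the protocol and Table 1, and to confirm that it covers falls and applies to both arms.

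**What to change.** 1. Open each weekly call in both arms, before any activity goal is set, with the same scripted and dated check: any new or worse cardiac symptoms since the last call, and any fall since the last call.
2. Ask regardless of perceived cause, and leave relatedness to the PI under IX.D. Reword the request in VII.D to cover any adverse event.
3. Escalate acute or unclear answers to the cardiologist or PI as needed under VII.D. Log all positive answers for the DSMB summaries by arm.
4. Add the fall question at Weeks 12 and 24, including the written or electronic packet used when a participant prefers not to answer by phone.
5. Add the check to Table 1 and the trainer manual, and exempt it there from the guidance in V.A (Training) on keeping calls to the exercise and MI topic.

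**Cost.** For 48 participants, about 9.6 to 19.2 trainer hours for the weekly check and 1.6 hours for the follow-up question, and more if more are randomized. Add some physician review time, a case-report field and more minor events to log. No new visits or staff are needed.

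**Limit.** The 12-week gap between symptom questions from Week 12 to Week 24 stays, because no calls are scheduled then. Closing it would need added contacts, which are not costed here.

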Membership of the DSMB. The DSMB will consist of members with extensive research experience in diabetes, mental health, and biostatistics of clinical trials. Three members will be [name] (Psychiatry), [name] [name] (Cardiology), and [name] (Biostatistics); all have agreed to serve in this role throughout the study. The DSMB Chairperson ([name]) will communicate by email and phone with the other members, and will coordinate formal, scheduled meetings of all members of the study and the PI.

Monitoring of Safety Data by the DSMB. Safety information for this study will be reported to the DSMB in an unblinded manner. A statistical penalty will not be assessed for the unblinded review of safety by the DSMB. Unblinded data will not be released to investigators

unless necessary for safety reasons.

Range of Safety Reporting to the DSMB. It is considered necessary that the DSMB review not only adverse events (AEs) and serious adverse events (SAEs), but other data that may reflect differences in safety between treatment groups. This includes treatment retention rates and reasons for dropout.

Serious Adverse Events. Expedited review will occur for all events meeting the definition of Serious Adverse Events (SAEs); i.e., any fatal event, immediately life-threatening event, permanently or substantially disabling event, or event requiring or prolonging inpatient hospitalization. This also includes any event that a study investigator or the DSMB judges to impose a significant hazard, contraindication, side effect, or precaution. All relevant information will be reported to the DSMB for each SAE including information about the event and its outcome, study group assignment, medications, the subject's medical history and current conditions, and any relevant laboratory data. Notification by e-mail and FAX transmittal of all related study forms shall be made to the DSMB. Information will be reviewed and a determination made of possible relevance to the study.

Non-Serious Adverse Events. At periodic intervals determined by the DSMB (e.g., quarterly during the study and then again at its completion), the DSMB will be provided with unblinded summaries of the numbers and rates of adverse events by treatment group. These reports will include types of events, severity, and treatment phase. Data on individual non-serious adverse events is not expected to be needed for this review.

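### The only stated adverse event request to participants is limited to study-related events, so falls, other non-serious events and non-cardiac care outside Partners may be under-counted

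*Combined protocol and SAP*

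**What the plan says.** **What is asked.** Section VII.D (Medical & psychiatric emergencies): "We will ask participants to report adverse events related to study participation they may have experienced at any time throughout the study". The next sentence deals with onward reporting: "Any adverse events will be reported to the PI and to the IRB according to Partners HRC guidelines". No other request to participants for adverse events is described. Table 1 has no adverse event row, and the Week 12 and Week 24 call content in Section V.A includes no general adverse event question.

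**Who judges relatedness.** Section IX.D: "when a serious or nonserious adverse event occurs, the PI will review the event to determine if it was possibly or definitely related".

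**What the DSMB receives.** Section IX.B, on serious events: "Expedited review will occur for all events meeting the definition of Serious Adverse Events (SAEs"), with no relatedness condition. On non-serious events: "the DSMB will be provided with unblinded summaries of the numbers and rates of adverse events by treatment group". The same section does not expect the DSMB to need data on individual non-serious events.

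**Blinding.** Section IV.C: "The interventionist and subjects will not be blind to the study condition". The follow-up assessor is blinded.

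**The named risk.** Section VII.D says of programs that promote activity: "there is an inherent potential physical risk imposed (e.g., falls, worsening cardiac symptoms").

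**The concern.** Sections IX.B and IX.D presuppose an unfiltered intake. Events come in, the PI judges relatedness, and the DSMB sees serious events individually and the rest as totals per arm. The request in Section VII.D applies a relatedness condition one step earlier, at the point where the participant is asked. Where an event has no other route to the study team, one that the participant does not connect with the study need never be reported.

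Participants know their arm, so the filter could act differently in the two groups. PP-MI sets a physical activity goal every week, while Section V.A describes the control as lacking specific activity goal-setting. A fall during a walk might therefore be linked to the program more readily in one arm than in the other. The DSMB receives non-serious events as summaries, so it could not see such a filter at work. Its judgement of risk against benefit is also the only stopping rule in Section IX.B.

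**Working it through.** No sample size, power or error-rate figure is involved, and the plan states no figure to reproduce. The check is to follow each kind of event from the participant to the PI or DSMB and ask whether the route depends on someone first calling the event study-related.

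**Routes that do not ask about cause**

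1. Section IV.B: an electronic alert tells study doctors of admissions and emergency visits, at Partners hospitals only.
2. Section V.A, follow-up calls: at Weeks 12 and 24 participants are asked about readmissions, but only cardiac ones.
3. Sections V.A and V.E: the WISE list records ten cardiac symptoms at baseline, Week 12 and Week 24. It is collected as an outcome, and no rule turns an answer into an adverse event report.
4. Sections V.A and V.E: HADS is given to everyone at the same times. Section VII.D adds an escalation procedure if suicidal thinking is reported.
5. Section IV.B, in-hospital consent: a release allows contact with treating clinicians at 12 and 24 weeks. No adverse event collection procedure is attached to it.
6. Section VII.D: acute symptoms that a participant mentions are acted on, related or not. This depends on their being volunteered.

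**Trace by event class**

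| Event | Main route | Depends on the restricted request? |
|---|---|---|
| Admission or emergency visit at a Partners hospital | Electronic alert | No |
| Cardiac readmission elsewhere | Week 12 and 24 question | No, though it may be learned late |
| Cardiac symptoms | WISE | No, but held as outcome data |
| Anxiety, depression | HADS | No, but held as outcome data |
| Non-cardiac admission or emergency visit outside Partners | Restricted request; perhaps treating clinicians | Mainly yes |
| Falls, musculoskeletal injury and other non-serious events | Restricted request, or volunteered on a call | Mainly yes |

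**Is care outside Partners realistic?** Section III.A requires a Partners-affiliated physician only for the outpatient recruitment route. Patients recruited in hospital at MGH or BWH need not have one, so some may receive later care elsewhere.

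**Result.** The last two rows are exposed and the first four are not. Of the two risks that Section VII.D names, worsening cardiac symptoms are partly captured by other means; falls are not.

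**The case against.** The strongest reply is that this is one loosely worded sentence in a plan that otherwise handles relatedness properly. The next sentence sends any adverse event to the PI and IRB, Section IX.D leaves the judgement to the PI, and serious events go to the DSMB whatever their cause. Both arms have weekly calls on which events can be mentioned, and the DSMB also sees retention and reasons for drop-out by arm. The trial is a feasibility pilot in which adverse event rates are not an endpoint.

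Much of this stands. A reader might infer that participants filter the safety data as a whole, or that non-serious events are never asked about. The documents do not support either reading. Four of the six event classes above reach the study without a question about cause, WISE and HADS ask about symptoms directly, and the Section VII.D request itself covers study-related non-serious events.

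A reader might also infer a bias in a known direction. That is not supported either. The control arm has activity content in Sessions 3 to 5, both arms receive a pedometer, and nothing in the documents shows how often participants in either arm would call an event study-related.

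What the reply does not remove is the gap in the last two rows. The sentence on onward reporting governs events that staff already know of; it does not widen what is asked. Volunteered reports are not systematic collection.

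**Conclusion.** The point holds in a limited form. The participant-facing request in Section VII.D is inconsistent with Sections IX.B and IX.D. Falls, other non-serious events such as musculoskeletal injury, and non-cardiac admissions or emergency visits outside Partners depend mainly on that request. They may be under-counted, and possibly unequally by arm. Neither size nor direction can be determined from the documents, and any numerical illustration would rest entirely on invented attribution rates.

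Two assumptions carry this. First, when a participant is asked for study-related events, the participant decides what counts; the protocol does not say so, but it names nobody else at that step. Second, no call script or form outside these documents already contains an open adverse event question. If one does, only the wording of Section VII.D needs changing.

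The feasibility aim is not threatened. The correction should be made because it is cheap and because the by-arm summary for the DSMB is hard to interpret without it.

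**What to change.** Reconcile Section VII.D with Sections IX.B and IX.D by replacing the request with wording such as:

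> *Participants in both arms will be asked the same scripted question about any new or worsened medical or psychological event, and any hospital or emergency visit, since the last contact, whether or not they think it is related to the study. The PI will then judge relatedness.*

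Also:

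- At Weeks 12 and 24, ask about all hospital admissions, not only cardiac ones. Carry the questions into the paper and e-mail versions of the follow-up that Section V.A allows.
- Protect the blinded assessor, because an account of an event could reveal the arm. Either have unblinded staff ask the question, or have the assessor's script tell participants not to mention their program.
- Add an adverse event row to Table 1.

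**Cost.** One question on calls already scheduled, more events to log, and a protocol amendment. Under Section IX.B the DSMB reviews proposed amendments, so both IRB and DSMB review are needed. If unblinded staff are to ask the question at Week 24, a short separate contact may be needed, since the scheduled call at that point belongs to the blinded assessor; the script option avoids this.
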